 - For add-on PD medication: percentage of patient on each PD medication (by drugs and class), total daily dose and levodopa equivalent Daily dose (LEDD), posology (number of times per day);
 - For LCIG infusion settings and substantial dose adjustments: total dose per day and specific for each type of dose (morning dose and continuous dose) and number of hours of infusion.
 - Tapering process: number of days required for the tapering process, total dose per day and posology for add-on PD medication prior to LCIG initiation, at LCIG initiation (titration) or during ongoing LCIG treatment
 - Main reasons for introduction or tapering of add-on PD medication or LCIG substantial dose adjustments
- Latency and duration of treatments data:
 - Number of days or months from LCIG initiation until LCIG is given as a monotherapy and the duration of LCIG monotherapy.
 - Number of days or months from LCIG initiation until the introduction or tapering of each PD medication, or until any LCIG substantial dose adjustments.

- LCIG monotherapy vs LCIG plus add-on PD medication data:
 - Healthcare Resource Utilization, as measured by Healthcare Resource Utilization Questionnaire (HCRU)
 - Patient's, caregiver's, and physician's overall preference on LCIG monotherapy vs. LCIG plus add-on PD medication, percentage of patient's and physician's preference for each of the options
 - Predictors for LCIG as monotherapy vs. LCIG plus add-on PD medication based on the patient's profile, including socio-demographics, clinical status (motor and nonmotor symptoms), Levodopa-equivalent dose (LED), PD medication and Quality of Life
 - Predictors for LCIG as monotherapy vs. LCIG plus add-on PD medications based on the physician's profile including experience as measured by, number of years on APD patient management, number of years using LCIG therapy, and number of patients on LCIG therapy

Population: Patients that may be enrolled in this study are adult patients with APD, who are under treatment with LCIG according to the local product label and specific reimbursement criteria. Decision to offer study participation has been made by their physician, based on meeting all of the inclusion criteria and none of the exclusion criteria.

A total of approximately 400 patients with APD will be included.

Patients must meet all of the following criteria:

- 1. Patients diagnosed with APD and on LCIG treatment for at least 12 months

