- 2. Patients must have been on continuous LCIG treatment for at least 80% of days in the preceding year
- 3. Patients must be treated by the same physician (PI or co-investigator) since the initiation of LCIG.
- 4. Decision to treat with LCIG was made and therapy was started by the physician prior to any decision to approach the patient to participate in this study
- Prior to any data collection, the patient, or legal authorized representative (LAR) has voluntarily signed an Authorization for Use/Disclosure of Data (AUDD)/informed consent form (ICF) according to national regulations after the study has been explained and the subject has had the opportunity to have questions answered

Patients must not be enrolled if they meet any of the following criteria:

- 1. Participation in a concurrent or a previous interventional clinical trial during which the patient was on LCIG therapy
- 2. Lack of motivation or insufficient language skills to complete the study questionnaires.

Variables: This is a PMOS with the objective of collecting data on the clinical practice of LCIG treatment upon treatment initiation and long-term follow-up.

Clinical Variables:

Information about the previous PD medication, and add-on PD medication and LCIG infusion settings will be retrospectively collected from patient's medical records.

Actual Parkinson's disease status and motor symptoms/motor complications will be measured using the following tools:

- Duration of OFF time and dyskinesia (hours during the day prior to the clinical visit) as reported by the patient
- UPDRS Parts III (motor evaluation) and IV (Treatment complication)

The following health outcomes will be measured using the following tools:

- UPDRS Part I (evaluation of mentation, behavior, and mood)
- UPDRS Part II (self-evaluation of the activities of daily living (ADLs))
- UPDRS Part V (Modified Hoehn and Yahr stage of severity of Parkinson's disease)
- PDQ-8 (Parkinson Disease Questionnaire) to evaluate PD patient's quality of life.

Non-motor symptoms including specific tool for sleep/daytime sleepiness, impulse control disorders and mental status will be measured using the following tools:

- Non-motor Symptoms Scale (NMSS)
- Parkinson's Disease Sleep Scale-2 (PDSS-2)
- Questionnaire for Impulsive-Compulsive Disorder in Parkinson's Disease-Rating Scale (QUIP-RS)
- Mini-Mental state Examination (MMSE)

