As progressive deterioration of the nigrostriatal dopaminergic transmission occurs, even complex oral drug regimens may become insufficient for symptom control [2]. Therefore, other therapeutic strategies have been developed, including treatments based on continuous drug delivery (CDD) [3-5], such as continuous subcutaneous apomorphine infusion therapy (CSAI), or levodopa-carbidopa intestinal gel (LCIG), or even surgical interventions such as implantation of deep brain stimulation (DBS) devices. However, in treatment options such as CSAI and DBS, continued use of PD medication appears to remain necessary for many APD patients. In many cases, CSAI does allow for withdrawal or tapering of other PD treatments such as COMT-inhibitors, dopamine agonists, and MAO-B inhibitors, as well as reductions of levodopa dosages. Still, CSAI is only rarely used as monotherapy as this is often limited by poor tolerability of high doses of apomorphine [28-32]. Studies on DBS treatment show that, even though DBS may enable reductions in the dosing of PD medication by 35-60%, patients can very rarely be managed without any additional therapy [28, 33, 34].

Levodopa-Carbidopa Intestinal Gel (LCIG)

Various levodopa CDD formulations (intravenous and enteral) have been under investigation for already more than 30 years [35-37]. Among the enteric CDD formulations, levodopa-carbidopa intestinal gel (LCIG) is the only formulation of LD and carbidopa which has been found to be suitable for continuous long-term intestinal infusion so far [38]. The LCIG system has been on the market for over 10 years, and is currently approved in more than 40 countries in the treatment of levodopa-responsive APD. In the

majority of countries, it is marketed by AbbVie (AbbVie Ltd, United Kingdom) under the trade names Duodopa[®] and Duopa[®] (in the United States).

The LCIG suspension is provided in 100 mL cassettes to be connected to an ambulatory pump (CADD-Legacy[®] 1400 portable pump) that delivers the cassette content directly into the duodenum. The LCIG infusion rate is programmable and can be adjusted in steps of 0.1 mL/h (equivalent to 2 mg levodopa/h). In addition, patients can self-administer extra doses during the day by pressing a dose button to infuse a pre-programmed bolus (usually 10 to 20 mg per bolus). Patients may also (if instructed to do so by their treating physician) adjust the amount of the extra dose according to their needs.

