9.5 Study Size

The primary objective of this PMOS is to estimate the percentages of APD patients on LCIG monotherapy right after LCIG initiation and at 3, 6, 9, and 12 months, respectively.

Sample size calculation was based on pre-defined precision of the estimators, expressed as the maximum length of the corresponding two-sided 95% confidence intervals. In order to achieve a precision of \pm 5% (i.e. the confidence intervals are not wider than 10%), and considering an underlying percentage of 50% (i.e. the percentage which leads to the largest sample size), at least 385 (evaluable) patients are necessary.

In this PMOS, only a small number of non-evaluable patients are expected. Therefore, it is planned to include a total number of approximately 400 patients.

9.6 **Data Management**

CRFs must be completed for each patient enrolled in this PMOS. These forms will be used to transmit information collected during the PMOS to AbbVie and regulatory authorities, as applicable. The CRF data for this PMOS are being collected with an electronic data capture (EDC) system, Rave[®], provided by the technology vendor Medidata Solutions Incorporated, NY, USA. The EDC system and the PMOS-specific eCRFs will comply with Title 21 CFR Part 11. The documentation related to the validation of the EDC system is available through the vendor, Medidata, while the validation of the PMOS-specific eCRFs will be conducted by AbbVie and will be maintained in the Trial Master File at AbbVie. The investigator will document patient data in his/her own patient files. Questionnaires filled in by the patients will be source data (e.g., QUIP-RS, PDQ-8, PDSS-2, BMQ). All eCRF data required by this protocol will be recorded in the EDC system. All data entered into the eCRF will be supported by source documentation, except for questionnaires that are completed by the physicians

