#### Clinical PD status immediately prior to / at LCIG initiation

- Duration of 'Off' state time during a 24h period (hours)
- Duration of dyskinesia during a 24h period (hours)
- Severity of dyskinesia
- Reason for LCIG start (multiple answers)
- Conduction of Nasojejunal test phase (yes, no)
  - If yes: reason (multiple answers)
  - If no: reason (multiple answers)
- Duration of titration calculated as date of titration finalization minus date of titration initiation +1
- Duration of LCIG treatment calculated as visit date minus date of LCIG initiation start +1
- Hospitalization for titration and PEG-J placement (yes, no)
- Hospitalization for PEG-J placement (yes, no)

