Backward elimination with a significance level of 0.05 will be applied to stepwise automatically select relevant predictors. Effect estimates and p-values will be given for each (potential) predictor.

For the second multivariable logistic regression model the following variables will be considered as potential predictors (i.e. independent variables):

Table 7-3: Potential predictors used for regression analysis 2

Variable	Range	Dichotomization/Grouping
Approximate number of APD patients treated per year	numeric	-
Years of LCIG experience	numeric	-
Years of DBS experience	numeric	-
Approximate number of APD patients treated with LCIG per year	numeric	-
Number of years physician has been working at the institution	numeric	-
Average number of PD and APD patients per year at center	numeric	-
Number of specialist physicians working with PD patients at center	Numeric	-
Origin of service at center	National health services, Private health services	National health services vs. Private health services
Average frequency of routine visits for APD patients on device aided therapy at center	< 1x/year, 1x/year, 2x/year, 3x/year, > 3x/year	≤ 1x/year vs. ≥ 2x/year
Country		
GNI	numeric	

Categorical predictors will be dichotomized / grouped as shown in Table 7-3 in order to simplify interpretation.

Backward elimination with a significance level of 0.05 will be applied to stepwise automatically select relevant predictors. Effect estimates and p-values will be given for each (potential) predictor.

For both regression models the Gross National Income (GNI) is defined as follows (source: https://data.worldbank.org/indicator/NY.GNP.PCAP.CD):

Country	GNI
Austria	45.44
Bulgaria	7.76
Canada	42.87
Czech Republic	18.16
Croatia	12.43
Estonia	18.19

Greece	18.09
Hungary	12.87
Ireland	55.29
Israel	37.27
Netherlands	46.18
Romania	9.97
Spain	27.18
Sweden	52.59

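### Years of LCIG experience in regression model 2 is tied by design to the patient's time on LCIG, which the model omits, so any start-year trend in monotherapy could partly appear as a physician effect

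*Protocol*

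**What the plan says.** **Eligibility.** Protocol 4.0 (Population) and 9.2.4, repeated in SAP 4.2.1, require "Patients diagnosed with APD and on LCIG treatment for at least 12 months" and give no upper limit. Protocol 7.0 notes that "The LCIG system has been on the market for over 10 years". Protocol 4.0 (Milestones) plans about 12 months of enrolment, so time on LCIG at the visit and calendar year of start carry nearly the same information.

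**Same-physician rule.** Criterion 3 states that "Patients must be treated by the same physician (PI or co-investigator) since the initiation of LCIG".

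**Models.** SAP 7.8 fits two logistic regressions of month-12 monotherapy, each with backward elimination at 0.05. Model 2 (Table 7-3) lists "Years of LCIG experience" with other physician and site variables, country and GNI. Neither Table 7-2 nor Table 7-3 contains start year or time on LCIG. The closest term in model 1 is the interval from diagnosis to LCIG start, which is not a calendar measure. Protocol 9.9 names country as the factor to allow for when predictors are analysed.

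**What is available.** The LCIG start date is collected (Protocol 9.2.7.7). SAP 6.3 derives "Duration of LCIG treatment calculated as visit date minus date of LCIG initiation start +1", and SAP 7.4 tabulates it overall and by month-12 monotherapy group, descriptively only.

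**The concern.** Criterion 3 puts a floor under physician experience. A physician with 3 years of LCIG use can contribute only patients who started in the last 3 years; one with 12 years of use can contribute starts from any of those years. In model 2, experience therefore stands in for the patient's start cohort.

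This matters only if month-12 monotherapy differs by start year. Three routes are possible:

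- **Practice:** add-on prescribing may have changed over the years.
- **Records:** SAP 6.4 counts an add-on with a missing reason as no monotherapy, but there is no rule for an add-on that was never recorded, which would count as monotherapy. Older records could shift the result in either direction.
- **Survivor selection:** only current LCIG patients are enrolled (Protocol 9.9), so early starters are long-term persisters.

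Predictors based on the physician's profile are a stated secondary objective. The risk is that a cohort difference is reported as an effect of physician experience.

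**Working it through.** **The plan's own figure.** Protocol 9.5 sets precision "expressed as the maximum length of the corresponding two-sided 95% confidence intervals", such that "the confidence intervals are not wider than 10" points, "considering an underlying percentage of 50"%. Then n = 1.96² × 0.5 × 0.5 / 0.05² = 384.15, rounded up to 385. The stated figure reproduces and is not in dispute.

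**Correlation created by criterion 3.** Let E be physician experience at the visit and T the patient's time on LCIG, so T ≤ E. The documents do not say to what date experience refers; it is taken here as the time of the study. They also give no distributions. Assume E uniform from 1.5 to 13 years and T uniform from 1 to E, with no attrition.

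- Var(E) = 11.5²/12 = 11.02, and mean E = 7.25.
- The mean of T given E is (1 + E)/2, so Cov(T, E) = 0.5 × 11.02 = 5.51.
- Var(T) = 0.25 × 11.02 + (11.02 + 6.25²)/12 = 2.76 + 4.17 = 6.93.
- Correlation = 5.51 / √(11.02 × 6.93) = 0.63.

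Simulation gives 0.63 for this case. It gives 0.40 to 0.63 across maximum experience of 10 or 13 years and attrition rates of 0, 0.15 or 0.30 per year. With the same-physician rule removed, the correlation is 0.

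**Effect on the experience coefficient.** Assumptions, none of them in the documents: 400 patients, 50 physicians with 8 patients each, 45% average monotherapy, no true physician effect, 1,500 runs per scenario. Month-12 monotherapy is regressed on E alone, then on E and T. Ranges cover the six combinations of attrition and maximum experience.

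| Trend, OR per later start year | Experience significant at 0.05 | False OR per 5 years of experience | Experience significant, T added |
|---|---|---|---|
| 1.00 (none) | 4.7-5.5% | about 1 | 3.9-5.5% |
| 1.05 | 6.7-12.2% | 0.88-0.95 | 4.5-5.8% |
| 1.10 | 10.7-34.1% | 0.78-0.90 | 4.3-5.7% |
| 1.20 | 21.8-80.7% | 0.65-0.82 | 4.2-5.7% |

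With the same-physician rule removed, the rate stays at 4-5% even with a trend.

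A second set of runs (80 physicians with 1.5-12 years of experience, 0-30% yearly attrition, 600 runs per scenario) states the trend in percentage points between starts 11 years and 1 year ago:

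- 40% vs 50%: significant in 5-10%.
- 30% vs 50%: 9-26%.
- With T in the model: 4-6%.

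The two scales agree. The move from 40% to 50% is an odds ratio of 1.5 over ten years, or 1.5^0.1 = 1.04 per year; 30% to 50% is 2.33^0.1 = 1.09 per year.

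**Share of a trend that transfers.** At OR 1.10, ln 1.10 = 0.0953. The weakest case gives |ln 0.900|/5 = 0.0211, a share of 0.22; the strongest gives |ln 0.784|/5 = 0.0487, a share of 0.51. So about a fifth to a half of the yearly trend passes to experience. The upper end matches the slope of 0.5 derived above.

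**With country in the model.** Both further sets of runs used 14 countries, the number in the SAP's GNI list. In one, country was kept and the rates were 8-22% at OR 1.10; adding T gave 4-6%. In the other, experience was assumed to cluster within countries, and country reduced the 20-point scenario from 13-26% to 6-12%.

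**Cost in precision.** The standard error for experience grows by about 1/√(1 − r²): 1.10 at r = 0.41 and 1.29 at r = 0.63.

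**Banded percentages.** The 95% half-width at 50% is 1.96 × √(0.25/200) = 6.9 points for two equal bands of 400 patients and 1.96 × √(0.25/133) = 8.5 points for three.

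**The case against.** The strongest reply is that everything depends on a trend the documents do not show. Nothing in them establishes that prescribing or record keeping changed over the years. With no trend the test keeps its level, and with a weak one it is close to it. This stands, and it makes the point conditional.

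The simulations fit experience without the rest of Table 7-3. Country, GNI, DBS experience and years at the institution could absorb part of the effect. For country this holds in part: it lowers the rate without reliably restoring 5%, and backward elimination may drop it. Criterion 3 also accepts a co-investigator, so the link loosens if the profile attached to a patient belongs to the other physician.

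Time on LCIG is already tabulated by month-12 monotherapy group, so a strong association would be visible, and SAP 7.10 allows extensions. That is a useful safeguard, but the table is unadjusted and an extension prompted by it would be post hoc.

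A reader might go further and infer that the pooled primary percentages are wrong because they depend on the mix of start years. The documents do not support that. The primary objective is descriptive, in consecutively enrolled current LCIG patients, and the pooled figure is its stated target. Nor is there a demonstrated need to force start year into model 1, which has no physician-experience term and for which no calculation was made.

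**Conclusion.** The point holds in conditional form. Criterion 3, with no maximum time on LCIG, ties physician experience to start cohort in model 2, and the model has no term to separate them. Under the assumed spreads the correlation is about 0.4-0.6. Combining both trend scales, the false-positive rate for experience is about 5-12% for a weak trend (10 points over 10 years, or OR 1.05 per start year) and about 9-34% for a moderate one (20 points, or OR 1.10). It is lower if country is retained.

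These sizes rest on assumed numbers of physicians, spread of experience, attrition and trend. It would be too strong to say that a change in practice will appear as a physician effect: no change is documented, and only about a fifth to a half of any trend would transfer. The case for acting is that the remedy uses a variable already derived and brings the rate to 3-6% in every scenario run.

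**What to change.** **SAP 7.8, model 2.** Keep time from LCIG start to visit (equivalently, start year) in the model whenever years of LCIG experience is assessed, so that backward elimination cannot remove it while experience is under test. State that its coefficient describes start cohort, meaning era plus survivor selection, and is not a pure practice trend. This also settles how experience is dated: experience at LCIG start equals experience at visit minus time on LCIG, so with time on LCIG in the model the experience coefficient is the same under either dating.

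**SAP 7.8, model 1.** Time on LCIG may be offered as a candidate predictor. Age in SAP 6.3 is age at visit and so contains time on LCIG, but this is an option only.

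**SAP 7.5, optional.** Show the primary percentages by two or three bands of start year as a descriptive supplement, with the same caution about survivor selection. The pooled FAS percentage remains the primary result.

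**Cost.** SAP wording, one model parameter and possibly one table, with no new data. The standard error for experience rises by about 10-29%, and banded percentages have half-widths of about 7 to 8.5 points against the planned 5.

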9.2 Setting

9.2.1 Number of patients to be enrolled

Approximately 400 adult patients diagnosed with APD, on current treatment with LCIG, and treated with LCIG for at least 12 months prior to study inclusion, will be enrolled in approximately 15 countries in Europe (Austria, Bulgaria, Croatia, Romania, Czech Republic, Estonia, Hungary, Ireland, Germany, Netherlands, Slovakia and Spain), Canada and Australia, among others, the final list of participating countries to be confirmed. All eligible patients at a given site will be enrolled consecutively in order to minimize selection bias.

9.2.2 Site Selection Criteria

The participating sites will be hospitals or clinics experienced in treating patients with APD, and with experience in LCIG treatment. Sites must have the ability to appropriately conduct the PMOS in accordance with applicable legal and regulatory requirements. Participating physicians should have been involved in the respective patient's management since initiation of LCIG therapy.

9.2.3 **PMOS Duration**

This PMOS consists of one single visit. The observational period is mainly retrospective and includes one cross-sectional study visit. Data gathered are derived from the time prior to initiation of LCIG therapy until the day of the study visit (see Figure 1).

[figure not shown]

Figure 1: Study Schematic

9.2.4 **Inclusion Criteria**

- 1. Patients diagnosed with APD and on LCIG treatment for at least 12 months
- 2. Patient must have been on continuous LCIG treatment for at least 80% of days in the preceding year
- 3. Patients must be treated by the same physician (PI or co-investigator) since the initiation of LCIG treatment
- 4. Decision to treat with LCIG was made and therapy was started by the physician prior to any decision to approach the patient to participate in this study
- 5. Prior to any data collection, the patient, or legal authorized representative (LAR) has voluntarily signed an Authorization for Use/Disclosure of Data (AUDD)/informed consent form (ICF) according to national regulations after the study has been explained and the subject has had the opportunity to have questions answered

9.2.5 **Exclusion Criteria**

- 1. Participation in a concurrent or a previous interventional clinical trial during which the patient was on LCIG therapy
- 2. Lack of motivation or insufficient language skills to complete the study questionnaires

9.2.6 **PMOS** conduct

Physicians will be provided with study information including a protocol, AUDD/ICF template, paper-based patient questionnaires, and access to the electronic Case Report Forms (eCRFs).

The study visit will take place during a regular clinic visit as foreseen per routine clinical practice.

Clinical data associated with this PMOS will be collected electronically (eCRF) via a web based electronic data capture (EDC) system. Access to the EDC system is granted by logging in with username and password. Patient/caregiver self-administered questionnaires will be completed on paper forms and then entered into the database by the designated contract research organization (CRO) GKM Gesellschaft für Therapieforschung mbH, Munich, Germany.

PMOS Procedures 9.2.7

Data for this PMOS will be collected during one single patient visit in accordance with routine clinical practice as indicated in Table 1, Summary of Assessments.

